Participants will receive a link to a dietary recall questionnaire (Intake24, <https://intake24.co.uk/>) via email the next morning after taking part in the study, which they will be prompted to complete before midnight that day. They will be asked to provide as much detail as possible on what they had for dinner, snacks, and drinks after the restaurant visit. Based on this information and salt values calculated by Intake24, we will estimate the total salt consumed by the participants for the rest of the day after the visit.

Other macronutrient intake

Total kcal, sugar, and saturated fat intake [i.e., other nutrients that are not the main warning focus] will be calculated based on the nutritional content of the order of the participant.

Additional measures

Food choice motives

The “health” subsection of the Food Choice Questionnaire (29) will be used to measure the extent to which health motives may influence participants’ food choices. The subsection consists of 6 items, e.g. “It is important to me that the food I eat on a typical day....is nutritious” answered on a 4-point Likert scale ranging from “Not at all important” to “Very important”. We will calculate the mean response for the six items.

Aim guessing

Participants are told that the study is about dining habits in restaurants. At the start of the post-meal assessments, participants will be asked what they think the aims of the study were (free text response). Any participant that guesses the study aims to be investigating the influence of food warning labels on food choice will be coded as being aware of study aims. One researcher will code awareness of aims ([name]) and a second researcher will independently verify the coding.

Study flow

Recruitment	
 - Participants will be recruited via online adverts, word of mouth, and an existing participant database maintained by researchers at the University of Liverpool. - A link to the screening questionnaire will be provided. (Appendix A) - Participants will be stratified by SEP, age, and sex. 				

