Appendix E – Post-exposure assessments

Please enter your participant ID. If you are unsure what this is, please ask the researcher.

Please select the letter which is circled on your sticker label. If you are unsure, please ask the researcher.

A (1)

B (2)

End of Block: Default Question Block

Start of Block: Aim guessing

What do you think was the aim of this study?

End of Block: Aim guessing

Start of Block: Food sharing

Did you share any of the food or drink items?

Yes (1)

No (2)

Display This Question:

If Did you share any of the food or drink items? = Yes

What items were shared? Please also give an estimation in % of how much of each item was shared.

Did you add any condiments (e.g., sauce, salt) to your food?

- Yes (1)
- No (2)

Display This Question:

If Did you add any condiments (e.g., sauce, salt) to your food? = Yes

What condiments did you add? Please also give an estimation in teaspoons of how much of each condiment was added.

End of Block: Food sharing

Start of Block: PME

Please consider the following statements in relation to the menu you ordered from.

Not at all (1) A little bit (2) Somewhat (3) Quite a bit (4) A great deal (5)

The menu made me concerned about the health effects of consuming items high in salt. (1)

The menu
made
consuming
items high in
salt seem
unpleasant. (2)

The menu
discouraged
me from
wanting to
consume
items high in
salt. (3)

 End of Block: PME**Start of Block: Attention check**

This question is an attention check, so please answer truthfully. How many times have you visited the planet Mars?

- Several times (1)
- Just once (2)
- Never (3)

End of Block: Attention check**Start of Block: Awareness**

Did you notice any warning labels next to any of the menu items when making your meal selection?

- Yes (1)
- No (2)

Display This Question:

If Did you notice any warning labels next to any of the menu items when making your meal selection?

= Yes

What did the label tell you about?

Healthy items (1)

Organic (2)

Calcium (3)

Sustainable (4)

Added sugars (5)

Vegetarian (6)

Unhealthy items (7)

Salt (8)

Fibre (9)

Gluten free (10)

None of these (11)

Not sure (12)

Display This Question:

If Did you notice any warning labels next to any of the menu items when making your meal selection?

= Yes

Please describe what the warning label said.

Page Break

Did you think about the salt content of the meals when making your selection?

Yes (1)

No (2)

End of Block: Awareness

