Start of Block: Additional assessments

Display This Question:

If Please select the letter which is circled on your sticker label. If you are unsure, please ask th... = B

Here is the menu you ordered from. The menu features salt warning labels next to items that exceed 50% of the daily recommended limit for salt intake: [menu B image]

Display This Question:

If Please select the letter which is circled on your sticker label. If you are unsure, please ask th... = A

Here is a slightly different version of the menu you ordered from. The menu features salt warning labels next to items that exceed 50% of the daily recommended limit for salt intake: [menu B image]

Did you learn something new from the salt labels on the menu?

Yes (1)

No (2)

Display This Question:

If Please select the letter which is circled on your sticker label. If you are unsure, please ask th... = B

Did the salt labels influence which food you ordered from the menu?

Yes (1)

No (2)

Display This Question:

If Did the salt labels influence which food you ordered from the menu? = Yes

How did the salt label influence your choice?

I avoided choosing a meal high in salt (1)

I chose a meal high in salt (2)

Other (please describe) (3) _____

Display This Question:

If Please select the letter which is circled on your sticker label. If you are unsure, please ask th... = A

Would the salt labels have influenced which food you ordered from the menu?

Yes (1)

No (2)

Display This Question:

If Would the salt labels have influenced which food you ordered from the menu? = Yes

How would the salt labels have influenced your choice?

- I would have avoided choosing a meal high in salt (1)
- I would have chosen a meal high in salt (2)
- Other (please describe) (3) _____

If the UK Government introduced policy requiring restaurant menu items high in salt to feature these labels, how would you feel?

- Strongly oppose (1)
- Oppose (3)
- Neutral (4)
- Support (5)
- Strongly support (6)

Please use this box to add any additional thoughts which you may have about the salt label.

End of Block: Additional assessments

Start of Block: Demographics

What is your age (in years)?

What is your sex? A question about gender identity will follow.

- Male (1)
- Female (2)

Which of the following best describes your gender?

- Man (1)
- Non-binary (2)
- Woman (3)
- Prefer to self-describe (4) _____
- Prefer not to say (5)

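### The questionnaire routes diners by an A/B letter they enter themselves, so a mis-tap asks the wrong perceived-influence question and the answer cannot be recovered

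*Combined protocol and SAP*

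**What the plan says.** Appendix E – Post-exposure assessments opens with the participant ID. The next item reads "Please select the letter which is circled on your sticker label" and offers A or B; a diner in doubt is told to ask the researcher. The aim-guess block follows ("What do you think was the aim of this study"), then food sharing, then PME, the attention check and the awareness items.

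The main text gives a different order. Under Additional measures, Aim guessing, it says: "At the start of the post-meal assessments, participants will be asked what they think the aims of the study were". The Post-meal assessments row of the Study flow table also starts with the aim guess. Neither place mentions a letter. The Aim guessing section also gives the cover story: "Participants are told that the study is about dining habits in restaurants".

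In the Additional assessments block of Appendix E, the letter is the only display condition for two things:

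- **Menu introduction.** Letter B gives "Here is the menu you ordered from". Letter A gives "Here is a slightly different version of the menu you ordered from". Both show the labelled menu.
- **Perceived influence.** Letter B gives "Did the salt labels influence which food you ordered from the menu". Letter A gives the hypothetical form, asking whether the labels would have influenced the order. The follow-up on how depends on which of these was shown.

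The Meal choice task row of the Study flow table says that condition is assigned in advance, by table, and that every participant gets a number to enter in each questionnaire.

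**The concern.** The diner is asked for something the study already knows, and the answer controls what they are asked next. A control diner who selects B is told they ordered from a labelled menu they never saw, and is asked whether its labels affected the order. A labelled diner who selects A is told they had a different menu and gets a hypothetical question about labels that were in front of them. Perceived influence is named in the primary objectives and listed under Primary outcomes. The introduction also frames the knowledge-gain item that follows it. According to the Missing data section every Qualtrics field requires a response, so a misrouted diner cannot leave the item blank.

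There is also a question of order. The aim guess is meant to test whether the cover story held. A circled letter with two options may hint at two groups just before that test. Diners coded as aware are removed in a sensitivity analysis, and a high rate (25% is given as an example) prompts a moderation analysis.

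**Working it through.** **1. What depends on the letter**

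| Item in Appendix E | Depends on the letter? |
|---|---|
| Aim guess, food sharing, PME, label awareness, salt awareness | No: same wording, same display |
| Menu introduction | Yes: two versions |
| Knowledge gain, policy support, free-text comments | Wording no; they follow the routed introduction |
| Perceived influence and its follow-up | Yes: actual against hypothetical |

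A mis-tap therefore corrupts perceived influence directly and knowledge gain through its framing. It leaves the PME and awareness answers as they are.

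**2. How many diners**

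The Sample size section gives a minimum of 260 (130 per condition). The mis-tap rate *e* is not in the documents; I assume 1% to 5%, equal in both arms. Misrouted diners = 260 × *e*:

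- 1%: 260 × 0.01 = 2.6, about 3
- 2%: 260 × 0.02 = 5.2, about 5
- 5%: 260 × 0.05 = 13

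If arm comes from the allocation list, a share *e* of each arm's perceived-influence answers are to the wrong question. Let *q* be the proportion of misrouted diners saying yes to the question they got, and *p* the proportion who would have said yes to the right one. The arm's reported proportion is then off by *e*(*q* − *p*), which cannot exceed *e*: at most 1 to 5 percentage points over the assumed range.

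**3. Whether the PME comparison is affected**

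The plan's own figure first. With d = 0.35, two-sided alpha 0.05 and 80% power, the normal approximation gives 129 per arm (258). The t-test gives 129.11, so 130 per arm and 260 in total, as stated. Power at 130 per arm is 0.806 (normal) or 0.803 (t).

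PME wording does not change with the letter, so a mis-tap affects this comparison only if the letter itself were used as the analysis arm. In that case, with SD 1 within arms, d becomes 0.35 × (1 − 2*e*) and the SD becomes √(1 + *e*(1 − *e*) × 0.35²). Power at 130 per arm (normal approximation) would be:

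| *e* | d | Power |
|---|---|---|
| 0 | 0.350 | 0.81 |
| 1% | 0.343 | 0.79 |
| 2% | 0.336 | 0.77 |
| 5% | 0.315 | 0.72 |

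The Statistical analysis section names label condition as the predictor without giving its source. No document says it is the letter, so this table is conditional and not part of the finding.

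**4. Whether the letter is needed**

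Allocation is fixed by table before the visit. The order form (Appendix D) holds each diner's study ID and the table number. The ID therefore leads to the table and the table to the allocation, without asking the diner.

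**The case against.** The strongest reply is that little is at risk. The sticker shows the letter, the screen tells doubtful diners to ask, and a researcher is on site. Errors can be found by matching ID to allocation, and the letter gives some cross-check on a mistyped ID. Perceived influence and knowledge gain are only described by condition; the plan sets no between-arm test for them. All of this stands and is why the point is minor. It does not remove the point: the prompt to ask does not catch a diner who taps the wrong letter with confidence, and finding the error later does not give the missing answer.

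A reader might infer that the letter reveals the design and biases PME. The documents do not support that. The letter screen mentions no menu, salt, label or group, and it is the same in both arms. A different menu version is first mentioned after PME and awareness. To be coded aware, a diner must guess that the study concerns warning labels and food choice; suspecting two groups is not enough. Labelled diners have already seen the labels, a much stronger cue, and the PME items themselves point to the menu and to salt. Ordering and eating are over before the iPad appears, so meal choice and salt eaten at the meal cannot be affected.

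It can be argued that only labelled diners could combine a two-group hint with labels they had seen, so that extra correct guesses would fall mainly in that arm and make the exclusion analysis unbalanced. That is plausible, but nothing in the documents sizes it. I did not have the information sheet or consent form (Appendices B and C), so I cannot say what diners already knew.

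**Conclusion.** The concern holds, at minor severity. A self-entered letter that the study does not need is the sole routing for the perceived-influence questions and the menu introduction, and a mis-tap produces a wrongly worded answer that cannot be repaired. At assumed error rates of 1% to 5% this affects about 3 to 13 of 260 diners. Separately, the letter sits ahead of an aim guess that the main text places first, and may hint at two groups; whether it changes the aim guess at all is unknown.

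Two larger conclusions should not be drawn. Bias in PME is not shown. Shrinkage of between-arm effects by a factor of 1 − 2*e* would arise only if the letter defined the analysis arm, which the plan does not state; the mis-tap rates are also assumptions, not figures from the documents.

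**What to change.** Remove the A/B item and the sticker. Have the researcher open the questionnaire with the study ID preloaded, using IDs that do not encode the condition, and let Qualtrics set the condition from the randomisation list as hidden data. The aim guess then becomes the first question the diner answers, as the main text describes. Add a sentence to the Statistical analysis section stating that label condition means the allocated arm from the randomisation list.

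The cost is a small set-up step in Qualtrics. Sample size, power and staffing do not change, since a researcher already runs the visit and the ID is already issued. The letter is lost as a cross-check on a mistyped ID; preloading the ID offsets this because the diner no longer types it.

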Appendix F – Additional demographic assessments

Please enter your participant ID. If you are unsure what this is, please ask the researcher.

Do you consider yourself to be a disabled person?

- Yes (1)
- No (2)
- Prefer not so say (3)

Do you have any physical or mental health conditions or illnesses lasting or expected to last for 12 months or more?

- Yes (1)
- No (2)
- Prefer not to say (3)

How would you describe your national identity? (select all that apply)

- British (1)
- English (2)
- Welsh (3)

- Scottish (4)
- Northern Irish (5)
- Other (please describe) (6) _____
- Prefer not to say (7)

What is your religion?

- No religion (1)
- Buddhist (2)
- Christian (including Church of England, Catholic, Protestant, and all other Christian denominations) (3)
- Hindu (4)
- Jewish (5)
- Muslim (6)
- Sikh (7)
- Any other religion (please describe) (8) _____
- Prefer not to say (9)

Do you identify as trans?

- Yes (1)

- No (2)
- Prefer not to say (3)

Which of the following best describes your sexual orientation?

- Asexual (1)
- Bi/bisexual (2)
- Gay or lesbian (3)
- Queer (4)
- Straight/heterosexual (5)
- Pansexual (6)
- I identify in another way (please describe) (7)

- Prefer not to say (8)

Are you currently? (select all that apply)

- Cohabiting or living with a partner (1)
- Divorced or civil partnership resolved (2)
- Married or in a civil partnership (3)
- Separated (4)

- Single (5)
- Other (specify, if you wish) (6) _____
- Widowed or surviving partner from a civil partnership (7)
- Prefer not to say (8)

In the last 12 months, have you taken any of the following types of leave? (select all that apply)

- Adoption leave (1)
- Maternity leave (2)
- Paternity leave (3)
- Shared parental leave (4)
- Parental bereavement leave (5)
- Other (specify, if you wish) (6) _____
- None of the above (7)
- Prefer not to say (8)

Do you have any caring responsibilities? (if you share care responsibilities equally then please answer as the primary carer)

- Yes (1)
- No (2)

Prefer not so say (3)

Display This Question:

If Do you have any caring responsibilities? (if you share care responsibilities equally then please... = Yes

Please select all that apply:

- Primary carer of a child or children (under 18 years) (1)
- Primary carer of a child or children who is disabled or has a health condition, or illness, or temporary care needs (under 18 years) (2)
- Primary carer or assistant for a disabled adult or adults (18 years and over) (3)
- Primary carer or assistant for an older person or people (65 years and over) (4)
- Secondary carer (another person carries out main caring role) (5)
- Prefer not to say (6)

What was the occupation of your main household earner when you were about aged 14?

- Modern professional & traditional professional occupations such as: teacher, nurse, physiotherapist, social worker, musician, police officer (sergeant or above), software designer, accountant, solicitor, medical practitioner, scientist, civil / mechanical engineer. (1)
- Senior, middle or junior managers or administrators such as: finance manager, chief executive, large business owner, office manager, retail manager, bank manager, restaurant manager, warehouse manager. Clerical and intermediate occupations such as: secretary, personal assistant, call centre agent, clerical worker, nursery nurse. (2)
- Technical and craft occupations such as: motor mechanic, plumber, printer, electrician, gardener, train driver. Routine, semi-routine manual and service occupations such as: postal worker,

machine operative, security guard, caretaker, farm worker, catering assistant, sales assistant, HGV driver, cleaner, porter, packer, labourer, waiter/waitress, bar staff. (3)

- Long-term unemployed (claimed Jobseeker's Allowance or earlier unemployment benefit for more than a year). (4)
- Small business owners who employed less than 25 people such as: corner shop owners, small plumbing companies, retail shop owner, single restaurant or cafe owner, taxi owner, garage owner. (5)
- Other such as: retired, this question does not apply to me, I don't know. (6)
- Prefer not to say (7)

